**11.7.2.2. Handling of Partial Dates**

Element	Reporting Detail
Concomitant Medications	
 
● Partial dates for any concomitant medications recorded in the CRF will be imputed using the following convention: 
 
○ If the partial date is a start date, a '01' will be used for the day and 'Jan' will be used for the month
 
○ If the partial date is a stop date, a '28/29/30/31' will be used for the day (dependent on the month and year) and 'Dec' will be used for the month.
 
 
 
● The recorded partial date will be displayed in listings.
 

Adverse Events	
 
● Any partial dates for adverse events will be raised to data management. If the full date cannot be ascertained, the following assumptions will be made: 
 
○ If the partial date is a start date, a '01' will be used for the day and 'Jan' will be used for the month.
 
○ However, if these results in a date prior to Week 1 Day 1 and the event could possibly have occurred during treatment from the partial information, then the Week 1 Day 1 date will be assumed to be the start date.
 
○ The AE will then be considered to start on-treatment (worst case).
 
○ If the partial date is a stop date, a '28/29/30/31' will be used for the day (dependent on the month and year) and 'Dec' will be used for the month.
 
 
 
● The recorded partial date will be displayed in listings.
 

**11.7.2.3. Handling of Missing Data for Statistical Analysis**

Element	Reporting Detail
Imputation	

• No imputation will be carried out for any parameters

## 11.8. Appendix 8: Values of Potential Clinical Importance

### 11.8.1. Laboratory Values

Haematology				
Laboratory Parameter	Units	Category	Clinical Concern Range	
			Low Flag (< x)	High Flag (>x)
Hematocrit	Ratio of 1	Male		0.54
		Female		0.54
		Δ from BL	↓ 0.075	
Hemoglobin	g/L	Male		180
		Female		180
		Δ from BL	↓ 25	
Platelet Count	x10  /L		100	550
While Blood Cell (WBC)				
Absolute Count	x10  /L		3	20
Neutrophil Count	x10  /L		1.5	
Lymphocytes	x10  /L		0.8	

Clinical Chemistry				
Laboratory Parameter	Units	Category	Clinical Concern Range	
			Low Flag (< x)	High Flag (>x)
Albumin	mmol/L		30	
Calcium	mmol/L		2	2.75
Creatinine	mmol/L	Δ from BL		↑ 44.2
Glucose (Fasting)	mmol/L		3	9
Potassium	mmol/L		3	5.5
Sodium	mmol/L		130	150
Total CO2	mmol/L		18	32

Liver Function				
Test Analyte	Units	Category	Clinical Concern Range	
ALT/SGPT	U/L	High	≥ 2x ULN	
AST/SGOT	U/L	High	≥ 2x ULN	
AlkPhos	U/L	High	≥ 2x ULN	
T Bilirubin	μmol/L	High	≥ 1.5xULN	
T. Bilirubin + ALT	μmol/L U/L	High	1.5xULN T. Bilirubin + ≥ 2x ULN ALT	

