6.3.6. Clinical Safety Laboratory Assessments

All protocol required laboratory assessments, as defined in [Table 8](#), must be conducted in accordance with the Laboratory Manual, and Protocol Time and Events Schedule.

Laboratory requisition forms must be completed and samples must be clearly labelled with the subject number, protocol number, site/centre number, and visit date. Details for the preparation and shipment of samples will be provided by the laboratory and are detailed in the SRM or the laboratory manual. Reference ranges for all safety parameters will be provided to the site by the laboratory responsible for the assessments.

If additional non-protocol specified laboratory assessments are performed at the institution's local laboratory and result in a change in subject management or are considered clinically significant by the investigator (e.g., SAE or AE or dose modification) the results must be recorded in the CRF.

Refer to the SRM for appropriate processing and handling of samples to avoid duplicate and/or additional blood draws.

Hematology, clinical chemistry, urinalysis and additional parameters to be tested are listed in [Table 8](#).

Table 8 Protocol Required Safety Laboratory Assessments

Hematology			
Platelet Count	RBC Indices:		Automated WBC Differential:
RBC Count	MCV	Neutrophils	
WBC Count (absolute)	MCH	Lymphocytes	
Reticulocyte Count	MCHC	Monocytes	
Hemoglobin			Eosinophils
Hematocrit			Basophils
Clinical Chemistry (Chemistry)			
BUN	Potassium	AST (SGOT)	Total and direct bilirubin
Creatinine	Chloride	ALT (SGPT)	Uric Acid
Glucose, fasting/non-fasting*	bicarbonate	GGT	Albumin
Sodium	Calcium	Alkaline phosphatase	Total Protein
Bile Acids			
*Glucose will be fasting for all screening, day 1 pre-dose, and follow-up assessments. Glucose will be non-fasting for all other time points.			
NOTE: Details of Liver Chemistry Stopping Criteria and Follow-Up Procedures are given in Section 4.5.1 and Section 11.2 (Appendix 3)			
Routine Urinalysis (UA)			
Specific gravity			
pH, glucose, protein, blood and ketones by dipstick			
Microscopic examination (within 120 minutes of collection)			
Triglyceride Assessment (Postprandial response)			
Triglycerides			
Exploratory Pharmacodynamics (Exploratory PD Labs)			
Cholesterol			
Triglycerides			
HDL			
LDL			
VLDL-Triglycerides (if feasible)			
Other screening tests			
HIV			
Hepatitis B (HBsAg)			

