**Table 4 Overview of Planned Clinical Laboratory Analyses**

Endpoint / Parameter/ Display Type	Absolute			Change from BL		
	Summary		Individual	Summary		Individual
	T	F	L	T	F	L
Chemistry						
Chemistry Changes from Baseline				Y		
Hematology						
Hematology Changes from Baseline				Y		
Urinalysis						
Urine Concentration Changes from Baseline				Y		
Urinalysis Dipstick Results	Y					
Hepatobiliary (Liver)						
Liver Monitoring/Stopping Event Reporting	Y		Y			
Matrix Display of Maximum LFT (ALT, AST, ALP, and Total Bilirubin) Values		Y				
Individual LFT (ALT, AST, ALP, and Total Bilirubin) Values versus Study Time by Treatment Group and Test		Y				
All Laboratory						
All Laboratory Data for Subjects with any Value of Potential Clinical Concern/PCI			Y			

Endpoint / Parameter/ Display Type	Absolute			Change from BL		
	Summary		Individual	Summary		Individual
	T	F	L	T	F	L
Laboratory Values of PCI			Y			

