**7.1.2.1. Clinical Laboratory**

Clinical laboratory results will be assessed for Part 1 and Part 2 separately. Laboratory evaluations will be summarized by the cohort of active treatments and pooling of placebo subjects within each part.

Clinical laboratory evaluations are divided into:

- **Haematology:** Platelet Count, RBC Count, WBC Count (absolute), Reticulocyte Count, Hemoglobin, Hematocrit, MCV, MCH, MCHC, Neutrophils, Lymphocytes, Monocytes, Eosinophils, Basophils;
- **Clinical Chemistry:** BUN, Creatinine, Glucose, Sodium, Bile Acids, Potassium, Chloride, bicarbonate, Calcium, AST (SGOT), ALT (SGPT), GGT, Alkaline phosphatase, Total and direct bilirubin, Uric Acid, Albumin, Total Protein;
- **Urinalysis:** Specific gravity, pH, glucose, protein, blood, ketones, Microscopic examination;
- **Liver Function Tests (LFTs):** total bilirubin, ALT.

Tables with descriptive statistics of change from baseline will be produced for all numerical tests for subjects with non-missing assessments. For categorical tests the number and percent of subjects for each category will be produced. Prior to analysis, all applicable numeric assessments will be converted to standard units.

Listing of all laboratory data for subjects with any value of PCI will be produced.

Listings of laboratory data with any value of PCI will be produced, too.

A listing will be created for subjects with any post baseline Liver Function Test (LFTs) with other Laboratory parameters, i.e. one of ALT and total bilirubin, classified as PCI..

Special figures, “matrix displays”, will be produced showing pairwise plots of the LFT values. To create these plots, the maximum value (over time) for each subject for each LFT will be calculated. Then for each pair of tests (e.g., total bilirubin vs ALT), each

subject will be plotted on the chart according to the maximum value of each. The subject markers (color and symbol) will be coded according to part /treatment.

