**11.5.3. Reporting Process & Standards**

Reporting Process
Software

 
• Version 6.2.1 (or higher) of WinNonlin will be used to determine PK parameters.
 
• Version 9.4 of SAS software will be used to create output displays (TLFs).
 

Analysis Dataset

 
• Analysis datasets will be created according to CDISC standards (SDTM IG Version 3.1 or higher & AdAM IG Version 1.1.)
 
• For creation of ADaM datasets (ADCM/ADAE), the same version of dictionary datasets will be implemented for conversion from SI to SDTM.
 

Generation of RTF Files

 
• RTF files will be generated for outputs (TLFs).
 

Reporting Standards
General

 
• The current GSK Integrated Data Standards Library (IDSL) will be applied for reporting, unless otherwise stated:                             
 
○ 4.03 to 4.23: General Principles
 
○ 5.01 to 5.08: Principles Related to Data Listings
 
○ 6.01 to 6.11: Principles Related to Summary Tables
 
○ 7.01 to 7.13: Principles Related to Graphics
 
 
 
• For placebo group, pooling of placebo subjects with each part is considered a general report rule, unless otherwise specified. All summary tables are for each part and all listings are for both parts combined into one, unless otherwise specified.
 

Formats

 
• All data will be reported according to the actual treatment the subject received unless otherwise stated.
 
• GSK IDSL Statistical Principles (5.03 & 6.06.3) for decimal places (DP's) will be adopted for
 

Reporting Standards	
reporting of data based on the raw data collected.	

 
Numeric data will be reported at the precision collected on the eCRF and laboratory reports.
 
	
Planned and Actual Time	

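### SAP 11.8.1 labels the albumin (<30) and creatinine (rise >44.2) flagging limits mmol/L, a unit that the printed numbers cannot carry

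*SAP*

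**What the plan says.** SAP 11.8.1 gives the laboratory PCI limits in three tables: Haematology, Clinical Chemistry and Liver Function. A value is flagged if it lies below the low limit or above the high limit.

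All seven rows of the Clinical Chemistry table carry the unit mmol/L. Two matter here:

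- Creatinine, as a change from baseline with a high limit: "Creatinine mmol/L Δ from BL ↑ 44.2".
- Albumin, as a low limit: "Albumin mmol/L 30".

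The neighbouring tables use other units. The Haematology table has "Hemoglobin g/L Male", and the Liver Function table gives total bilirubin in μmol/L.

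On units in general, SAP 7.1.2.1 says: "Prior to analysis, all applicable numeric assessments will be converted to standard units". It does not list those units. SAP 11.5.3 applies the sponsor's IDSL reporting standards and adds a rule on precision: "Numeric data will be reported at the precision collected on the eCRF and laboratory reports". The programming note for Tables 3.13/3.14 mentions repeating some chemistry parameters in conventional units. The analyte lists in Protocol 6.3.6 (Table 8) and SAP 7.1.2.1 carry no units. Protocol 6.3.6 leaves reference ranges to the laboratory: "Reference ranges for all safety parameters will be provided to the site by the laboratory responsible for the assessments".

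The limits feed two outputs. SAP 7.1.2.1 states "Listing of all laboratory data for subjects with any value of PCI will be produced", which is Listing 20. The row "Laboratory Values of PCI" in SAP Table 4 is Listing 21, restricted to the flagged values. Table 4 plans laboratory PCI output as listings only.

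**The concern.** A flagging limit works only if number and unit belong together. As blood concentrations, a creatinine rise of 44.2 mmol/L and an albumin of 30 mmol/L are out of scale by about three and two orders of magnitude respectively. No other section of the protocol or SAP gives a unit for either analyte, so the unit column in Appendix 8 is the only one a programmer will find in these documents.

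At stake is whether Listings 20 and 21 pick out the intended results. The two errors would act in opposite directions: the albumin limit would catch everything and the creatinine limit nothing.

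**Working it through.** **Inputs from the documents.** Creatinine rise limit 44.2 and albumin low limit 30, both labelled mmol/L (SAP 11.8.1). The SAP does not derive these limits, so there is no plan figure to reproduce. The check is whether number and unit are compatible.

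**Assumptions, not in the documents.** Molar mass of creatinine 110-115 g/mol; molar mass of albumin 65-69 kDa, that is 65-69 g/mmol.

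**Formula.** Mass concentration = molar concentration × molar mass.

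**Creatinine as printed.** mmol/L × g/mol gives mg/L; dividing by 10 gives mg/dL.
- 44.2 × 110 / 10 = 486.2 mg/dL
- 44.2 × 115 / 10 = 508.3 mg/dL

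In other terms, 44.2 mmol/L is 44,200 μmol/L. From an assumed baseline of 50-120 μmol/L, the flag would need a level (120 + 44,200)/120 = 369 to (50 + 44,200)/50 = 885 times baseline. It could never fire.

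**Creatinine read as μmol/L.** The results are 1,000 times smaller: 0.486-0.508 mg/dL, close to a round 0.5 mg/dL.

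**Albumin as printed.**
- 30 mmol/L × 65 g/mmol = 1,950 g/L
- 30 mmol/L × 69 g/mmol = 2,070 g/L

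That is about 2 kg of albumin per litre. Any real result expressed in mmol/L lies far below 30, so the low flag would always fire.

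**Albumin read as g/L.**
- 30 / 69 = 0.435 mmol/L
- 30 / 65 = 0.462 mmol/L

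The label is therefore off by a factor of about 65-69 for albumin and 1,000 for creatinine. No value in the assumed ranges rescues either row.

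**The rest of the table.** Calcium, glucose, potassium, sodium and total CO2 have limits that are plausible in mmol/L. That fits one unit having been applied to the whole block, although this cause is an inference.

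**Could text extraction explain it?** A lost micro sign could turn μmol/L into mmol/L for creatinine. It could not turn g/L into mmol/L for albumin. The Clinical Chemistry table itself contains no micro sign to compare, but μmol/L survives in the separate Liver Function table, which makes a loss in the creatinine cell improbable.

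**Effect on the outputs, by how the comparison is programmed.**

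| Comparison | Albumin flag | Creatinine flag | Listings 20 and 21 |
|---|---|---|---|
| Values expressed in mmol/L | every result | never | Listing 20 admits every subject with an albumin result; Listing 21 shows every albumin value and no creatinine rise |
| Bare numbers, data held in g/L and μmol/L | works | works | unaffected |

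The SAP does not say which applies.

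**The case against.** The strongest reply is that the error may never touch an output. To compare albumin in mmol/L, a programmer would have to convert it with a molar mass that the SAP does not supply, and nothing in the documents asks for that. If the laboratory reports g/L and μmol/L and the program uses the bare numbers, the flags work and only the labels are wrong. The unit convention may also lie in the IDSL standards that SAP 11.5.3 invokes, which are not available here. Both points stand. They limit the consequence but do not make the labels right.

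Three stronger readings are tempting, and the documents do not support them.

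- *All subjects would be listed as having a value of concern.* Ten Part 1 cohorts of 8 (Cohort 9 was cancelled) and three Part 2 cohorts of 8 give 10 × 8 + 3 × 8 = 104 planned subjects. That is an improbable upper bound, because it depends on the albumin conversion just described. The fault would also be obvious at the first dry run.
- *A creatinine signal would be lost.* A missed flag would be silent in the PCI listings, but only there. SAP 7.1.2.1 summarises change from baseline for all numerical tests (chemistry in Tables 3.13/3.14), and Protocol 8.4.1 includes minimum and maximum in descriptive summaries unless stated otherwise. A large rise would show as a maximum. Under Protocol 11.3.1, laboratory abnormalities that the investigator judges clinically significant are generally recorded as adverse events, whatever the PCI flag.
- *The SAP has miscalculated, and both cells are certainly wrong.* No SAP calculation is involved. Certainty holds for albumin; for creatinine a lost micro sign is improbable but cannot be excluded from the extracted text.

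**Conclusion.** The point holds as a minor unit-label error in two PCI limits. Albumin below 30 cannot be in mmol/L. A creatinine rise above 44.2 cannot be in mmol/L either, and that cell is very likely printed wrongly. Both conclusions rest on assumed molar masses, but they hold across the whole range used and do not depend on an exact value.

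The consequence is conditional and confined to Listings 20 and 21. It ranges from none to a complete failure of these two flags, depending on a programming choice that the SAP leaves open. Tables 3.13/3.14 do not use the limits, the liver criteria are multiples of the upper limit of normal, and none of the pharmacokinetic models draws on these rows. The error still merits correction because these are operational thresholds, not background text.

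**What to change.** Correct the unit cells for albumin and creatinine in SAP Appendix 8 before Listings 20 and 21 are programmed. The printed numbers need not change: they are usable as g/L for albumin and μmol/L for creatinine. Those units come from general knowledge and not from the documents, so first confirm them against the laboratory's reporting units and the analysis dataset.

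A phrase in 7.1.2.1 naming the corrected Appendix 8 units as those used for PCI flagging would remove the remaining ambiguity, but it is optional.

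The cost is two cells and one unit check. No new data, analysis or output is needed.

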**11.8.2. ECG**

ECG Parameter	Units	Clinical Concern Range	
		Lower	Upper
Absolute			
Absolute QTc Interval	msec	> 450 	
		> 450 	≤ 479 
		≥ 480 	≤ 499 
		≥ 500 	
Absolute PR Interval	msec	< 110 	> 220 
Absolute QRS Interval	msec	< 75 	> 110 
Change from Baseline			
Increase from Baseline QTc	msec	> 60 	
	msec	> 30 	≤ 59 
	msec	≥ 60 	

**NOTES:** [Remove footnotes for RAP development]

[2] Represent standard ECG values of PCI for HV studies

[3] Represent further subdivisions of ECG values for analysis whereby the RAP team needs to decide whether these need to be generated in addition to standard ECG values being flagged. IF not required, then delete.

**11.8.3. Vital Signs**

Vital Sign Parameter (Absolute)	Units	Clinical Concern Range	
		Lower	Upper
Systolic Blood Pressure	mmHg	< 85	> 160
Diastolic Blood Pressure	mmHg	< 45	> 100
Heart Rate	bpm	< 40	> 110

Vital Sign Parameter (Change from Baseline)	Units	Clinical Concern Range			
		Decrease		Increase	
		Lower	Upper	Lower	Upper
Systolic Blood Pressure	mmHg	≥ 20	≥ 40	≥ 20	≥ 40
Diastolic Blood Pressure	mmHg	≥ 10	≥ 20	≥ 10	≥ 20
Heart Rate	bpm	≥ 15	≥ 30	≥ 15	≥ 30

**NOTES:** [Remove footnotes for RAP development]

Represent further subdivisions of BP & HR for analysis whereby the RAP team needs to decide whether these need to be generated in addition to standard absolute BP & HR values being flagged. IF not required, then delete.

## 11.9. Appendix 9: Pharmacokinetic / Pharmacodynamic Analyses

### 11.9.1. Overview of Planned Pharmacokinetic (PK) / Pharmacodynamic (PD) Analyses

The PK/PD analyses described in this appendix is purely for documentation purpose only and report is outside of scope of this RAP/CSR.

The PK/PD analyses will be based on the PK/PD population, unless otherwise specified.

The relationship between drug pharmacokinetics and pharmacodynamic endpoints (e.g. TG AUC) will be explored.

The PK parameters are perhaps included AUC(0-∞), AUC(0-t), Cmax, and Cmin in Part 1, AUC(0-∞) on Day 1, AUC(0-tau), Cmax, and Cmin on Days 1 and 14 in Part 2. PD parameters are %change from baseline (Day -1) of TG AUC(1-12) and TG AUC(2-5) as well as with the adjusted post dose TG values calculated AUC(1-12) and TG AUC(2-5).

All summary tables and figures are for each part separately and all listings are for both parts combined into one, unless otherwise specified.

Exposure-Response Analysis between the PK parameters and PD parameter will be conducted separately for Part 1 and Part 2.

PK parameters are PK AUC and PK concentrations including Cmax and other concentrations as appropriate. The PD parameters are %change from baseline (Day -1) of TG AUC(1-12) and TG AUC(2-5) as well as with the adjusted post dose TG values calculated AUC(1-12) and TG AUC(2-5).

[Table 9](#) below provides an overview of the planned PK/PD analyses with full details of data displays being presented in [Appendix 12](#): List of Data Displays.

**Table 9 Overview of Planned PK/PD Analyses**

PK Parameter / PD Parameter	Untransformed Stats Analysis		
	T	F	L
PK Parameter / PD Parameter			
Correlation between PD Parameter TG AUC and PK Parameters by Treatment and Day (in Part 2)	Y	Y	
Emax Model Applied for PD Parameter TG AUC and PK Parameters by Treatment and Day (in Part 2)	Y	Y	Y

**NOTES :**

- T = Table, F = Figure, L = Listing, Y = Yes display generated.

**11.9.2. Statistical Analyses of Postprandial Triglyceride**

**11.9.2.1. Correlation Analysis**

The correlation between PK parameters and PD parameters will be analysed by spearman method.

Summary and Figures of correlation between percent (%) change from baseline of TG AUC [AUC(1-12), AUC(2-5), as well as Corrected AUC(1-12) and Corrected AUC(2-5)] and PK parameters [AUC(0-inf), Cmax, Cmin on day 1 in part 1, AUC(0-inf) on day 1 in part 2, Cmax and Cmin on days 1 and 14 in part 2] by treatment and day will be produced.

Figure of the TG Level vs. dose by day may be also produced.

Sample code can be used as follows:

```
Proc corr data=analy Spearman;
  Var parameter1;
  with parameter2;
run;
```

**11.9.2.2. Exposure – Response Analysis**

A 4 parameter Emax model will be applied between PD parameter and PK parameters.

The PK parameters are probably included AUC, Cmax, and other concentration as appropriate.

The PD parameter is percent (%) change from baseline in TG AUC.

The exposure-response analysis will be conducted separately for part 1 and part 2.

Analyses of percent (%) change from baseline in TG AUC data will be carried out using MIXED effect model.

**Emax Model description:**

Primary Statistical Analyses
Endpoint(s)

 
Part 1: Percent change from baseline in TG AUC at Day 1
 
Part 2: Percent change from baseline in TG AUC at Day 1 and Day 14
 

Model Specification

 
First: A 4 parameter Emax model will be used as specified below:
 
 
Endpoint = <math>E_0 - E_{max} [ PK\ parameter^m / (IC_{50}^m + PK\ parameter^m) ] + Subject + random\ error</math>

**Primary Statistical Analyses**

where:

- PK parameter are the PK parameters we would investigate: AUCLast, Cmax, Cmin and Clast
- $E_0$  is the percent change from baseline in TG AUC when the PK parameter is 0
- $E_{max}$  is the maximum achievable percent change from baseline in TG AUC
- $IC_{50}$  is the PK parameter level which achieves 50% of the  $E_{max}$
- $m$  is the slope/hill constant

Sample SAS code will be provided later.

Depending upon the adequacy of model fitting some parameter may need to be analyzed on log scale (e.g.  $IC_{50}$ ,  $E_{max}$ ).

If issues arise with the model fitting using a 4 parameter model then maybe made based on the data.

**Model Checking & Diagnostics**

- Refer to [Appendix 1: Model Checking and Diagnostics for Statistical Analyses](#).

**Model Results Presentation**

- The results of the Emax model will be tabulated by part and day (in part 2). Tables will include the point estimates of the parameters, their 95% confidence interval and p-value. The  $IC_{50}$ ,  $IC_{90}$  (PK parameter level which achieves 90% of the  $E_{max}$ ) and model fit diagnostics such as the AIC and  $R^2$  value will also be presented for each PK parameter.
- The results of the Emax model will be presented graphically by part and day (in part 2). Predictions will be plotted against the raw values of percent change from baseline in TG AUC against the relevant PK parameter.

**11.10. Appendix 10: Model Checking and Diagnostics for Statistical Analyses**

**11.10.1. Statistical Analysis Assumptions**

Dose Proportionality (Part 1 and Part 2)

Endpoint(s)	
 
• Part 1:                             
 
○ AUC(0-t), AUC(0-∞), and Cmax applied to all single dosing active treatments
 
○ AUC(0-∞) applied to multiple dosing active treatments
 
 
 
• Part 2: AUC(0-∞) on Day 1, AUC0-T and Cmax on Day 1 and Day 14
 

Analysis	
 
• Power Model
 

 
• Model assumptions will be applied, but appropriate adjustments maybe made based on the data.
 
• The Kenward and Roger method for approximating the denominator degrees of freedom and correcting for bias in the estimated variance-covariance of the fixed effects will be used.
 
• Distributional assumptions underlying the model used for analysis will be examined by obtaining a normal probability plot of the residuals and a plot of the residuals versus the fitted values (i.e. checking the normality assumption and constant variance assumption of the model respectively) to gain confidence that the model assumptions are reasonable.
 
• If there are any departures from the distributional assumptions, alternative models will be explored using appropriate transformed data.
 
	

Accumulation Ratio (Part 2)

Endpoint(s)	
 
• (R0, RCmax)
 

Analysis	
 
• Mixed Model
 


 
• Model assumptions will be applied, but appropriate adjustments maybe made based on the data.
 
• When the G matrix does not converge, the alternative variance covariance structure will be used.
 
• The Kenward and Roger method for approximating the denominator degrees of freedom and correcting for bias in the estimated variance-covariance of the fixed effects will be used.
 
• Distributional assumptions underlying the model used for analysis will be examined by obtaining a normal probability plot of the residuals and a plot of the residuals versus the fitted values (i.e. checking the normality assumption and constant variance assumption of the model respectively) to gain confidence that the model assumptions are reasonable.
 
• If there are any departures from the distributional assumptions, alternative models will be explored using appropriate transformed data.
 
	

